#### Toxicity assessments

The proportion of patients experiencing grade 3 or 4 toxicity will be compared between the two treatment arms using the chi-squared test. When cell frequencies are less than 5, Fisher's exact test will be used. The chi-squared test for trend will also be used to compare all toxicity scores.

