#### 8.3 Assessment of compliance

An assessment of medication compliance will be made by the principal investigator or delegated research team, member on Day 7 and at the end of the treatment course based on verbal answers given to direct questioning and a count of untaken medication on Day 15. These data will be entered into the Case Report Form.

Following completion of the patient's IMP treatment period any unused medication will be returned to the site Pharmacy department for the IMP accountability log to be updated. Patients who take the study drug for < 8 days in the 14 day treatment period will be considered 'non-compliant'. All patients will continue to be followed up according to the study protocol regardless of compliance.

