# 14. Pharmacovigilance

#### 14.1 Definitions

**Adverse Event (AE)** — Any untoward medical occurrence in a patient or clinical investigation subject administered a pharmaceutical product and which does not necessarily have to have a causal relationship with this treatment.

An adverse event (AE) can therefore be any unfavourable and unintended sign (e.g. an abnormal laboratory finding), symptom or disease temporally associated with the use of a medicinal product, whether or not considered related to the medicinal product. Pre-existing conditions should only be reported as an adverse event if the condition worsens by at least 1 CTCAE grade. As the IMP has a short half-life, we would expect drug clearance within 24 hours of stopping the IMP.

As part of pharmacovigilance, adverse event data will be collected from the day 1 of IMP dose until 4 weeks following the end of the IMP 14 day treatment schedule. This coincides with the D42 post surgical review.

**Adverse Reaction (AR)** — All noxious and unintended responses to a medicinal product related to any dose should be considered adverse drug reactions.

**Serious Adverse Event (SAE)** or Serious Adverse Reaction (SAR) — any untoward medical occurrence that at any dose:

- Results in death,
- Is life-threatening,
- Requires inpatient hospitalisation or prolongation of existing hospitalisation,
- Results in persistent or significant disability/incapacity or
- Is a congenital anomaly/birth defect.

Medical and scientific judgement should be exercised in deciding whether expedited reporting is appropriate in other situations, such as important medical events that may not be immediately lifethreatening or result in death or hospitalisation but may jeopardise the patient or may require intervention to prevent one of the other outcomes listed in the definition above. These should also usually be considered "serious".

Suspected Unexpected Serious Adverse Reaction (SUSAR) — an Adverse Reaction which is classed in nature as both serious and unexpected

An 'Unexpected Adverse Reaction' is when both the nature and severity of the event is not consistent with the reference safety information available for the IMP in question.

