**Unlikely** — there is little evidence to suggest there is a causal relationship (e.g. the event did not occur within a reasonable time after administration of the trial medication). There is another reasonable explanation for the event (e.g. the participant's clinical condition, or other concomitant treatments).

**Unrelated** — there is no evidence of any causal relationship.

**Not Assessable** — Note if this description is used the sponsor will assume the event is related to the IMP until follow up information is received from the investigator to confirm a definitive causality assessment.

Any SUSAR assessed as related to the IMP will need to be reported to the Sponsor irrespective of how long after IMP administration the reaction has occurred.

Expectedness should be based solely on the available RSI for the IMP and will be described using following categories :

**Expected** — an AE that is classed in nature as serious and which is consistent with the information about the IMP listed in the RSI or clearly defined in this protocol.

**Unexpected** — an AE that is classed in nature as serious and which is not consistent with the information about the IMP listed in the RSI.

The completed AE Log will be sent to Sponsor upon request and/or every 2 months.

The Chief Investigator (CI) will respond to any SAE queries raised by the Sponsor as soon as possible. Follow up reports must continually be completed within acceptable timeframes and sent to the sponsor as detailed above until the reportable event is considered resolved.

Notification of deaths

All deaths will be reported to the Sponsor irrespective of whether the death is related to disease progression, the IMP or an unrelated event.

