#### 17.2 Endpoints

## 17.2.1 Primary endpoints

The primary endpoint for the main comparison between the artesunate treatment and placebo arms will be persistent disease or disease recurrence, two years following surgery. All analyses will be made on an intention to treat basis, although per protocol analyses will also be reported. Statistical significance will be assumed at the 5% level unless otherwise indicated.

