## Surgical morbidity/mortality

The proportion of patients experiencing an adverse event in relation to surgical morbidity/mortality will be compared between the two treatment arms using the chi-squared test. When cell frequencies are less than 5, Fisher's exact test will be used. The chi-squared test for trend will also be used to compare rates of adverse events. Length of hospital stay will be reported as a mean.

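### The named toxicity proportion, grade 3 or 4, leaves out grade 5 as written; a lesser point is that the blanket intention-to-treat sentence keeps never-dosed patients in its denominator

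*Protocol*

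**What the plan says.** Section 17.3.3.3, Toxicity assessments, defines the comparison in three sentences. The first names the endpoint and the test: "The proportion of patients experiencing grade 3 or 4 toxicity will be compared between the two treatment arms using the chi-squared test". The second covers sparse tables: "When cell frequencies are less than 5, Fisher's exact test will be used". The third adds a wider comparison: "The chi-squared test for trend will also be used to compare all toxicity scores".

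The analysis population comes from Section 17.2.1: "All analyses will be made on an intention to treat basis, although per protocol analyses will also be reported". That sentence stands under the primary endpoint but is worded for every analysis. Section 17.3.3.3 makes no exception for toxicity.

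Section 14.1 ties collection to dosing: "adverse event data will be collected from the day 1 of IMP dose until 4 weeks following the end of the IMP 14 day treatment".

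Toxicity is graded by CTCAE Version 5.0 (Sections 6.12 and 8, Appendix 4). Tolerability is a secondary objective in Section 5, and drug-related toxicity and adverse events are listed as separate secondary endpoints in Section 5.1.

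**The concern.** A severe-toxicity proportion should count the worst outcomes. Section 6.12 describes grade 4 as life-threatening, and in the CTCAE that the protocol adopts the grade above it, grade 5, is death. A numerator limited to grades 3 and 4 therefore places a patient whose only severe event was fatal among those without severe toxicity. The protocol allows for such events: Section 14.1 lists death first among the seriousness criteria, and Section 11.4 names anaphylaxis, serious arrhythmia and neutropenic sepsis as events that might need unblinding.

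The denominator raises a lesser question. A randomised patient who never takes a tablet has no defined adverse event window under Section 14.1, yet under Section 17.2.1 stays in the denominator as a patient without toxicity. Never-starters are plausible. The product is allocated at dispensing with a start date tied to surgery (Section 11.3), and Section 12.3 foresees cancelled surgery.

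What is at stake is whether the main severe-toxicity comparison describes tolerability correctly. The efficacy result is not affected.

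**Working it through.** **No toxicity figure to reproduce.** The protocol states no expected toxicity rate and no expected share of never-dosed patients. Its sample size (54 events, 168 patients) concerns recurrence and is not in question here.

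**Inputs.**
- 100 patients per arm: 200 patients, 1:1 (Sections 7.1 and 11.2).
- 5% significance (Section 17.2.1), taken as two-sided (assumption).
- True grade 3 to 5 toxicity of 15 of 100 on artesunate and 5 of 100 on placebo (assumption).
- 1, 2 or 3 artesunate patients whose only severe record is a fatal event, and none on placebo (assumption).
- 2%, 5% or 10% of each arm never dosed (assumption).

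**Numerator.** No observed cell is below 5, so on observed counts the protocol's own test is chi-squared. With 100 per arm, difference d and pooled proportion p, the uncorrected statistic is d² / [p(1 − p) × 2/100]. For 15 against 5, p = 0.10 and d = 0.10, so the statistic is 0.01 / 0.0018 = 5.56.

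| Fatal cases not counted | Counts compared | Chi-squared | p, chi-squared | p, Fisher |
|---|---|---|---|---|
| 0 | 15 v 5 | 5.56 | 0.018 | 0.032 |
| 1 | 14 v 5 | 4.71 | 0.030 | 0.051 |
| 2 | 13 v 5 | 3.91 | 0.048 | 0.081 |
| 3 | 12 v 5 | 3.15 | 0.076 | 0.126 |

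Each omitted case lowers the artesunate rate by one percentage point. Under chi-squared the result crosses 5% only at the third omission; under Fisher's test, at the first.

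**Denominator.** If a share u of each arm never starts and has no toxicity recorded, the intention-to-treat rate is the rate in dosed patients × (1 − u). At u = 5%, 0.15 × 0.95 = 0.1425 and 0.05 × 0.95 = 0.0475.

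| Never dosed | Rates, intention to treat | Power, intention to treat | Power, dosed patients only |
|---|---|---|---|
| 2% | 14.7% v 4.9% | 64.7% | 64.8% |
| 5% | 14.25% v 4.75% | 63.1% | 63.4% |
| 10% | 13.5% v 4.5% | 60.5% | 61.0% |

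The rate ratio stays at 3, because both arms shrink by the same factor. Power differs by 0.1, 0.3 and 0.5 points.

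**The per-protocol alternative.** Section 17.2.1 also promises per-protocol analyses, but the protocol does not define that set. Its only compliance threshold is fewer than 8 days of drug in the 14-day course (Section 8.3). Section 8, Dosage modifications, discontinues treatment after a related Grade 3/4 reaction. If the per-protocol set follows the compliance threshold, a patient stopped in the first week because of toxicity drops out of it. Neither set named in the protocol suits a toxicity analysis.

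**The case against.** The strongest reply is that fatal events are not lost to the trial. The trend test covers all toxicity scores and is not limited to grades 3 and 4. Surgical morbidity and mortality have their own between-arm comparison ("The proportion of patients experiencing an adverse event in relation to surgical morbidity/mortality will be compared between the two treatment arms using the chi-squared test"), overall survival is analysed, and Section 14.2 states: "All deaths will be reported to the Sponsor irrespective of whether the death is related to disease progression, the IMP or an unrelated event". This stands. A reader might infer that fatal toxicity disappears from the safety evaluation, and the protocol does not support that: the gap is in one proportion. The reply does not close the gap, however. A trend test is a different comparison, the surgical comparison concerns surgical events, and reporting to the sponsor is not a comparison of arms.

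The numerator also counts patients who experienced grade 3 or 4 toxicity, not those whose maximum grade was 3 or 4. A patient with a recorded grade 3 or 4 event who later dies still counts. That narrows the omission to patients whose only severe record is fatal. The omission applies to either arm, and the table shows the least favourable case, with every such death on artesunate.

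On the denominator, the sentence stands under primary endpoints, adverse event capture is already tied to dosing, and a safety population could sit in an analysis plan that is not shown. Its absence alone is therefore no finding. What remains is that the protocol states a rule for all analyses without an exception, and a later safety set would have to contradict it.

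Two further inferences lack support. One is that misdispensed bottles distort the toxicity rate: no misdispensing is described, and Section 11.3 requires a dispenser and a checker, with labels kept on the accountability record and checked by the monitor. The other is that the same rules govern the interim safety and tolerability looks: Sections 17.3.3.1 and 17.5 give neither a grade rule nor a denominator for them.

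**Conclusion.** The point holds and is minor. As written, the named proportion omits grade 5, so a patient whose only severe toxicity is fatal is classed as free of severe toxicity in that comparison. The error favours whichever arm has the death. Under the assumed 15 against 5 per 100, one omission changes the rate by one point and leaves the chi-squared result significant; three would not. These rates and numbers of deaths are illustrations. Section 6.8 reports two Grade 3 cases in the pilot but not the arm sizes, so no toxicity rate can be taken from it.

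The intention-to-treat denominator is the smaller part. A reader might infer that it hides a toxicity signal. With 2% to 10% never dosed equally in both arms, the assumed 15% falls by 0.3 to 1.5 points, the rate ratio does not change, and power differs by at most 0.5 points. Nothing here shows that a conclusion of the trial depends on either rule.

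**What to change.** In Section 17.3.3.3, Toxicity assessments, define the numerator as patients whose maximum grade is 3 or higher (grades 3 to 5), each patient counted once.

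In the same place, state as an exception to Section 17.2.1 that toxicity and adverse events are analysed in patients who took at least one dose, by product actually received. Keep intention to treat for efficacy.

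The cost is two phrases. No data collection, sample size or visit changes. The downside is that the reported toxicity rate may be slightly higher.

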#### Locoregional failure

Patterns of locoregional failure will be reported descriptively.

#### Quality of life

The functional and symptomatic scales of the EORTC quality of life questionnaires (EuroQol EQ-5D, EORTC QLQ C-30, EORTC QLQ-CR29) will be examined by calculating the differences in measurements from baseline. The standard EORTC recommended methods will be used to calculate function and symptomatic scores. The nature of the variable which quantifies this EORTC score will be investigated and summary statistics will be presented for values at baseline and post treatment. A multivariable regression type analysis will be conducted with post-treatment scores and pre- treatment (baseline) scores as an outcome and groups defined by the interventions as explanatory variables. Additional explanatory variables such as age, gender, disease stage may also be included. Missing data will be investigated in a similar fashion as previously described.

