#### 11.2 Randomisation procedure

Participants recruited to the study will be randomised to receive either artesunate or placebo 1:1. Randomisation will be by a computer-generated code. An unblinded randomisation list will be provided to each participating site and held in Pharmacy or held by a study coordinator that is not directly involved in the study. Following completion of the study the participant treatment allocation list held in the site Pharmacy files will be anonymised prior to collection by the Clinical Trials Monitor. The anonymised lists will be handed over to the statistician to facilitate data analysis.

All patients will be given a study specific 24 hrs emergency contact card immediately after being randomised. The card includes details of the Trial: Study title, details of IMP, patient trial number, CI/PI's contact details along with out of hours contact details in case of emergency.

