#### **12.2 Baseline assessments**

All participants who consent to enter the study and fulfill all of the eligibility criteria will be entered onto the Subject ID log and be assigned a unique subject ID and undergo a review at the 1st study visit prior to randomisation and commencing the artesunate/placebo treatment course. A full medical and concomitant medication history will be taken. Staging investigations will be reviewed and vital signs and baseline blood samples will be performed. Baseline blood tests will include FBC, urea and electrolytes, liver function tests (LFT), and carcinoembryonic antigen (CEA). A pre-treatment blood sample will be taken for study molecular analyses. Patients will be asked to complete EORTC validated quality of life questionnaires (EuroQol EQ-5D, EORTC QLQ C-30, QLQ-CR29). Potential female participants of child bearing age must have a negative pregnancy test.

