# 17.3 Sample size and recruitment

#### 17.3.1 Sample size calculation

We performed our sample size calculation largely based on inferences drawn from our pilot Phase I study (Krishna *et al.*, 2015). The input assumes that the analysis would be conducted using a univariate Cox proportional hazard survival model from the time of surgery to the first disease recurrence with one binary covariate representing treatment groups (artesunate or placebo). We calculated that a minimum sample size of 168 patients is necessary to test a hazard ratio (HR) of 0.56 for the intervention versus placebo. This value is within the confidence intervals estimated in our phase I study (Krishna *et al.*, 2015) and somewhat between the point estimate in the worse case scenario inference in the paper and a value of 0.7 commonly circulated in oncology clinical trials. For this Phase II study, we set the power at 0.8 and accepted a type one error of 0.1 for a one-sided test.

- 1) The null nypothesis H0: HR=0.56 (equivalent ≤)
- 2) The alternative hypothesis H1: HR>0.56

These settings would result in a sample size of 168 patients. Inflating this sample size by 15-20% to allow for loss at follow-up would result in approximately 194-202 patients. We believe that 200 patients therefor represents a feasible and achievable target given our time and financial constraints.

The rationale and sensitivity analyses for these calculations are outlined below. The general setting is that of a survival analysis where the event is defined as the first disease recurrence after surgery.

A cohort of Stage II/III colorectal cancer patients undergoing surgery will be randomised as per recruitment to receive the artesunate intervention or placebo. Patients will be followed-up for 5 years following surgery. The minimum sample size to test a hazard ratio (HR) of 0.56 for the intervention vs. placebo group is based on:

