#### 17.3.2 Planned recruitment rate

NeoART aims to randomize 200 participants in total. We have faced challenges meeting our recruitment target in. We have therefore discussed these issues with the DMC and TSC in the UK and a decision has been made to combine the data from the UK with a mirror study in Vietnam (NeoART-Vietnam) and Malaysia (NeoART-Malaysia). Although different study populations, these are mirror studies in terms of trial protocol, study procedures and Investigational Medicinal Product source. The target recruitment in the UK will now be 34, Vietnam will be 46 and Malaysia will be 120 patients and a target trial recruitment of 200 patients.

In Malaysia, 5 Ministry Of Health, Universiti Malaya are ready to open the trial. We aim to recruit 8-12 participants to the study per month in each sites in Malaysia over 24 months.

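### The quality-of-life regression lists the baseline score as an outcome, does not name it as a covariate, and leaves the treatment contrast undefined

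*Protocol*

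**What the plan says.** The Quality of life paragraph in protocol Section 17.3.3.3 points to two analyses.

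- It opens by saying that the scales "will be examined by calculating the differences in measurements from baseline".
- It then specifies a model: "A multivariable regression type analysis will be conducted with post-treatment scores and pre- treatment (baseline) scores as an outcome", with "groups defined by the interventions as explanatory variables".

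On further regressors it says: "Additional explanatory variables such as age, gender, disease stage may also be included". The baseline score is not among these examples. The paragraph mentions no time term, no group-by-time term and no common baseline mean, and it does not say which coefficient or difference is the treatment effect.

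The questionnaires are completed at the baseline visit, which Section 12.2 places before randomisation and the start of treatment, and again on Day 7 and Day 14 (Section 12.3 and Appendix 2).

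**The concern.** The baseline score is measured before treatment and allocation is randomised, so the expected group difference at baseline is zero. Such a variable is useful as a covariate, because it explains between-patient variation in the later score. Placed among the outcomes with only treatment group to explain it, it either brings a null difference into the estimate or leaves its explanatory power partly or wholly unused.

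The impact of artesunate on quality of life is a stated secondary objective (Section 5). Dilution would not be neutral here: a real worsening of quality of life on treatment would look smaller than it is, in a trial whose rationale rests partly on good tolerability.

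**Working it through.** The protocol gives no standard deviation, effect size, correlation or power for quality of life, so there is no figure of its own to reproduce. Its one sample-size figure (168, Section 17.3.1) belongs to the primary endpoint and does not bear on this point.

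**Inputs from the protocol**
- Allocation: "Participants recruited to the study will be randomised to receive either artesunate or placebo 1:1" (Section 11.2). The expected baseline difference is 0.
- Size: "NeoART aims to randomize 200 participants in total" (Section 17.3.2), so n = 100 per arm before losses.
- Significance level 5% (Section 17.2.1), taken here as two-sided.

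**Assumptions not in the protocol**
- The same standard deviation σ at both times, and a baseline/post correlation ρ of 0.3, 0.5 or 0.7.
- For the power illustration only, a true post-treatment effect δ = 0.4σ.

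**Estimate and variance under each reading**, with variance in units of 2σ²/n:

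| Analysis | Estimates | Variance | ρ = 0.3 | ρ = 0.5 | ρ = 0.7 |
|---|---|---|---|---|---|
| ANCOVA, baseline as covariate | δ | 1 − ρ² | 0.91 | 0.75 | 0.51 |
| (a) One group coefficient over both scores | (0 + δ)/2 | (1 + ρ)/2 | 0.65 | 0.75 | 0.85 |
| (b) Change from baseline, or unconstrained group-by-time | δ | 2(1 − ρ) | 1.40 | 1.00 | 0.60 |
| (c) Separate coefficient for each score | δ | 1 | 1.00 | 1.00 | 1.00 |

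**Variance relative to ANCOVA**
- (b): 2(1 − ρ)/(1 − ρ²) = 2/(1 + ρ), giving 1.54, 1.33 and 1.18.
- (c): 1/(1 − ρ²), giving 1.10, 1.33 and 1.96.
- (a): (1 + ρ)/2 exceeds 1 − ρ² only when ρ > 0.5. The damage under this reading is the halved estimate, which does not depend on ρ.

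**Power illustration.** The standard error is √(2/100) = 0.1414 (in units of σ) times the square root of the variance factor, and power is Φ(estimate/SE − 1.96). For ANCOVA at ρ = 0.5, SE = 0.1414 × √0.75 = 0.1225 and power is Φ(0.4/0.1225 − 1.96) = 90.4%.

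| Analysis | ρ = 0.3 | ρ = 0.5 | ρ = 0.7 |
|---|---|---|---|
| ANCOVA | 84.3% | 90.4% | 97.7% |
| (a) | 41.8% | 37.2% | 33.5% |
| (b) | 66.7% | 80.7% | 95.5% |
| (c) | 80.7% | 80.7% | 80.7% |

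A simulation of 4,000 trials at each ρ, with 100 per arm, agrees. The mean estimate was 0.19 to 0.20 under (a) and 0.39 to 0.40 under the others. The empirical standard errors were within 0.002 of the formulas.

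A fourth model also has baseline as an outcome: the constrained longitudinal model, with a common baseline mean and a group-by-time term. By standard theory it is unbiased and about as efficient as ANCOVA (this was not simulated). The Quality of life paragraph does not describe it.

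**The case against.** The strongest defence is that the sentence is ambiguous, not wrong. The paragraph opens with differences from baseline, and the model sentence speaks of a single outcome, so the two scores may simply mean the pre/post difference. Change-score analysis is valid in a randomised trial, and preferring ANCOVA is then a matter of efficiency. At ρ = 0.7 the gap in the illustration is small (95.5% against 97.7%). The covariate list is open-ended: adding baseline to a change-score model would give the same group estimate as ANCOVA. Time terms and the exact contrast are commonly left to a statistical analysis plan, which is not at hand.

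Much of this stands. The change-score reading is at least as plausible as stacking, and the missing time structure alone would not be a finding. What remains is what the protocol does state: baseline is assigned to the outcome side and is absent from the named covariates. An analysis plan that used ANCOVA would have to depart from that sentence.

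A reader might infer three stronger things, which the text does not support:

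- **That the planned analysis halves the quality-of-life effect.** This follows only if both scores share one group coefficient with no time structure, and the protocol does not say that they will.
- **That having baseline as an outcome is an error in itself.** The constrained longitudinal model shows that it is not.
- **That variance is inflated on every reading.** Under the shared coefficient it exceeds that of ANCOVA only when ρ > 0.5.

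Nor can one assume a baseline score for every patient. Participants are asked to complete the questionnaires, and Section 15.2 anticipates missing ones.

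**Conclusion.** The point holds as a defect in how the model is specified. On each of the three readings that the sentence supports as written, the estimate is either diluted or less precise than one adjusted for baseline. Dilution, to about half, occurs on one reading only. On the other two the estimate is unbiased, and the variance penalty is 18% to 54% (change score) or 10% to 96% (unadjusted post-treatment comparison) over correlations of 0.3 to 0.7. Those ranges rest on assumed correlations and equal standard deviations. The power figures rest further on an assumed 0.4 SD effect and 100 complete cases per arm.

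The consequence is confined to a secondary endpoint with no stated power target. The primary analysis and the sample size are untouched. This is a free improvement, not a threat to the trial's main conclusion.

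**What to change.** Replace the model sentence in the Quality of life paragraph with one of two explicit specifications:

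1. The post-treatment score as outcome (Day 14, or Day 7 and Day 14 as repeated measures), with treatment group and the baseline score as covariates.
2. A constrained longitudinal model with baseline, Day 7 and Day 14 scores as outcomes, a common baseline mean for the two arms, and a group-by-time term.

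In either case, name the post-treatment group difference as the treatment effect, and state that change-from-baseline summaries are descriptive. Age, gender and disease stage can stay as further covariates.

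The cost is a sentence or two of protocol text. It needs no new data, visits or participants.
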